9.3.1 Exposures

Patients will be assigned to one of the following mutually exclusive study cohorts based on the index pharmacy claim: Stiolto Respimat or Trelegy Ellipta. Exposure measures will be based on pharmacy dispensing of the two medications under study, namely Stiolto Respimat or Trelegy Ellipta, over a follow-up period, beginning the index date and lasting up to one year from index date. Discontinuation for index medication will be defined as a gap in index medication of \geq 45 days (sensitivity analysis with \geq 30 days can be included) following the runout of days' supply (discontinuation date = runout prior to the gap in therapy). Switch in index medication will be defined as a pharmacy fill for \geq 30 consecutive days of a non-index maintenance medication (switch date = first date of the new treatment regimen). Switch includes any other change in use of index medication by active ingredient, inclusive of a change to a different combination therapy (ICS/LABA FDC, different LAMA/LABA or LAMA/LABA/ICS FDC) change from a FDC to a free form combination therapy with mono LAMA plus mono LABA, or mono ICS plus mono LABA, or mono LAMA plus mono LABA plus mono ICS or a change to a monotherapy.

Individuals in the study cohort will be followed from the index date until the earliest of the date of a switch in treatment, addition of an ICS for the Stiolto Respimat group, discontinuation of the index COPD maintenance treatment, the end of the study period, or the end of continuous health plan eligibility. Main analyses will be further limited to the first 12 months after index date, with sensitivity analyses considering all available data.

All patients will be required to be continuously enrolled in the health plan for a minimum of 12 months. The 12 months prior to and including the index date (index date – 364 through index date) will be used to assess baseline characteristics. The period starting the day after the index date, up to a maximum of 12 months duration (index date +1 through index date +365) will be used to assess exacerbation, pneumonia, HCRU and cost outcomes. Patients will be censored at the earliest of the following: discontinuation of the index medication (Stiolto or Trelegy), switch to a non-index medication, disenrollment from the health plan, 12-months following the index date, or the end of the study period.

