Patients will be followed the index date to record time to first incidence of exacerbations, record time to first incident case of pneumonia, and HCRU. The analysis will be, "on treatment", analysis. Patients will be followed from the index date until the earliest of the first occurrence of outcome event, switch in index treatment (Stiolto or Trelegy), discontinuation of index treatment (Stiolto or Trelegy), the end of the study period, the end of continuous health plan eligibility, or (for main analyses) one year after index date. Hazard ratios and their 95% CI from proportional hazards models will be used to assess differences in the risk of COPD exacerbation and pneumonia.

Proprietary confidential information © 2022 Boehringer Ingelheim International GmbH or one or more of its affiliated companies

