9.2.2 Study Population

Patients initiating Stiolto, or Trelegy will be identified using pharmacy claims (database). The date of the first prescription claim (on or after 15th September 2017) will be defined as the index date. Patients will be required to have a diagnosis of COPD (ICD-9-CM: 491.xx, 492.xx, 496.xx; ICD-10-CM: J41-J44) on two separate medical claims. Patients 40 years or older will be included in the study. Patients will be required to have continuous enrolment for 12 months prior to the index date. Patients will be excluded if they show any use of COPD maintenance medications (ICS, LABA or LAMA in any combination), during the baseline period of six months pre-index date. This will satisfy the criteria for being considered as treatment naive. Patients with two separate medical claims with a diagnosis of asthma, lung cancer, interstitial lung disease, or cystic fibrosis during the study period will be excluded. Using propensity score matching (PSM) technique, we will develop matched cohorts of patients between Stiolto initiators and Trelegy initiators. We will conduct 1:1 matching using nearest neighbour matching approach with a caliper of 0.2. Exacerbation will be defined as a COPD hospitalization (severe exacerbation) or Emergency Department (ED) visit (severe exacerbation) with COPD, or use of approved respiratory antibiotics (e.g., Azithromycin) \pm Oral CorticoSteroids (OCS) medications within ± 7 days of the

Proprietary confidential information © 2022 Boehringer Ingelheim International GmbH or one or more of its affiliated companies

office/outpatient visit (moderate exacerbation) as the primary diagnosis. Multiple exacerbations occurring within 14 days of each other will be considered as a single exacerbation and will be per the higher severity.

Patients will be followed after the index date to record time to first incidence of exacerbations, record time to first incident case of pneumonia, and HCRU. The analysis will be, "on treatment", analysis. Patients will be followed from the index date until the earliest of the first occurrence of outcome event, switch in index treatment (Stiolto or Trelegy), discontinuation of index treatment (Stiolto or Trelegy), the end of the study period, the end of continuous health plan eligibility, or (for main analyses) one year after index date. Hazard ratios and their 95% CI from proportional hazards models will be used to assess differences in the risk of COPD exacerbation and pneumonia.

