9.7.1 Main analysis

Analyses will be presented comparing Stiolto vs Trelegy overall after PSM matching and stratified as follows if the sample size allows (at least 15% in each strata):

• Low history of exacerbation: 0 inpatient (i.e., severe exacerbations) and 0-1 outpatient events (i.e., moderate exacerbations)

Proprietary confidential information © 2022 Boehringer Ingelheim International GmbH or one or more of its affiliated companies

• High history of exacerbation: ≥1 inpatient (i.e., severe exacerbations) or ≥2 outpatient events (includes ED)

We will describe the formation of the study cohort. Patient characteristics at baseline in patients treated with Stiolto and patients treated with Trelegy will be assessed separately using standard descriptive statistics.

Propensity scores including both pre-specified and data-derived variables will be then calculated. Balance of patient characteristics between the cohorts will be described before and after propensity score application and compared using standardized differences. For each Stiolto patient, a Trelegy patient with the closest available propensity score will be selected. Nearest neighbor matching method with a caliper of 0.2 will be utilized. Standardized differences greater than 0.10 (10%) will be taken to indicate imbalance, and these variables will also be included in outcome models, categorized as appropriate.

For the analysis of the primary objective, a Cox proportional hazard regression model will be used to perform an as-treated analysis that assesses the effect of first line maintenance medication with Stiolto versus the first line maintenance medication with Trelegy on the time to first COPD exacerbation. This estimates the HR of a COPD exacerbation associated with Stiolto use relative to Trelegy use, along with 95% CI. Based on the days' supply post index date, allowing a grace period of 45 days following the end of days' supply to account for intermittent use.

Stratified analyses will be using the same approach as the main analysis. Calculation of propensity scores will be repeated within the subset of the cohort with available results to create weighted populations suitable for these stratified analyses.

The analysis of the secondary objective related to the risk of pneumonia will also be assessed using Cox proportional hazard regression models with an as-treated approach, like that of the primary analysis.

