APPENDIX 2: COPD-RELATED RESPIRATORY MEDICATIONS AND CLASSES

Drug Class	Subclass	Medication
Maintenance		aclidinium
medications	Inhaled long-acting anti-	glycopyrrolate
	muscarinic	revefenacin
	agents (LAMA)	tiotropium
		umeclidinium
		arformoterol
	Long-acting β-agonists (LABA)	formoterol
		indacaterol
		olodaterol
		salmeterol
		beclomethasone
		budesonide (both inhaler and nebulizer)
	Inhaled corticosteroids (ICS)	ciclensonide
		flunisolide
		fluticasone
		mometasone
		triamcinolone

Boehringer Ingelheim Non-Interventional Study (NIS) Protocol BI Study Number 1237-0121

c38026921-01

Proprietary confidential information © 2022 Boehringer Ingelheim International GmbH or one or more of its affiliated companies

Drug Class	Subclass	Medication	
		aclidinium/formoterol	
	Inholod I AMA/I ADA	glycopyrrolate/formoterol	
	innaled LAMA/LABA	indacaterol/glycopyrrolate	
	combination	tiotropium/olodaterol	
		umeclidinium/vilanterol	
		budesonide/formoterol	
	Inhaled ICS/LABA	fluticasone/salmeterol	
	combination	fluticasone/vilanterol	
		mometasone/formoterol	
	Inholod ICS/LADA/LAMA	Budesonide/glycopyrrolate/formoterol	
	initiated ICS/LABA/LAWA	fumarate ¹	
	combination	Fluticasone/umeclidinium/vilanterol	
	Mathulyanthing	aminophylline	
	(intravenous oral)	dyphylline	
	(intravenous, orar)	theophylline	
	PDE-4 inhibitor (oral)	roflumilast	
Rescue		albuterol	
medications		bitolterol	
	Short-acting B-agonists	isoetharine	
	(SABA) (inhalation oral)	isoproterenol	
		levalbuterol	
		metaproterenol	
		pirbuterol	
	Short-acting anti-muscarinic	ipratropium	
	Agents (SAMA) (inhalation)		
	SAMA/SABA (inhalation)	ipratropium/albuterol	
		betamethasone	
		dexamethasone	
	Oral corticosteroids $(OCS)^2$	hydrocortisone	
		methylprednisolone	
		prednisolone	
		prednisone	

¹This medication was FDA approved for maintenance treatment of COPD on 24 July 2020, which is outside of the study time period, and will not be included in this study.

²Including tablets, oral solutions, elixirs, etc. Injectable corticosteroid medications will not be included.

Proprietary confidential information © 2022 Boehringer Ingelheim International GmbH or one or more of its affiliated companies

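### All specified comparative Cox analyses are as-treated, one of four follow-up lists adds a Stiolto-only stop at ICS addition, and no visible sensitivity analysis relaxes this possibly informative censoring

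*Combined protocol and SAP*

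**What the plan says.** Follow-up is described in four lists.

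- **Section 9.1** (text after Figure 1): the stopping events include "switch in index treatment (Stiolto or Trelegy), discontinuation of index treatment (Stiolto or Trelegy"), the end of the study period, loss of eligibility and one year. ICS addition is not named.
- **Section 9.2.2**: the same content ("switch in index treatment (Stiolto or Trelegy), discontinuation of index treatment (Stiolto or Trelegy), the end of the study period"). ICS addition is not named.
- **Section 9.3.1, first list**: a switch, discontinuation, end of study or eligibility, and also "addition of an ICS for the Stiolto Respimat group".
- **Section 9.3.1, second list**: "Patients will be censored at the earliest of the following: discontinuation of the index medication (Stiolto or Trelegy), switch to a non-index medication", then disenrollment, 12 months or study end. ICS addition is not named.

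A switch, in either arm, is a fill of at least 30 "consecutive days of a non-index maintenance medication (switch date = first date of the new treatment regimen"). The ICS-addition stop has no such minimum.

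Section 9.7.1 says the primary Cox model is "used to perform an as-treated analysis", and the pneumonia model follows the same approach. The sensitivity analyses named are an optional 30-day gap (9.3.1), an extension beyond 12 months "with sensitivity analyses considering all available data" (9.3.1), results by exacerbation severity (9.3.2.1) and optional work on prognostic covariates (9.7). Section 9.9 promises a bias analysis without giving a method.

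**The concern.** A Cox model assumes that, within each arm, patients who are censored have the same future risk as those who remain. Section 7 says that escalation to triple therapy is recommended after further exacerbation, so adding an ICS to Stiolto is plausibly a marker of higher risk. A Trelegy patient already takes an ICS and cannot make the equivalent step. If higher-risk Stiolto patients leave the risk set while similar Trelegy patients stay, the Stiolto hazard is understated.

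The endpoints differ in exposure. For time to first exacerbation, a step-up after the first event does no harm, because the event has already been counted; only step-up before it matters. Pneumonia, exacerbation counts, resource use and costs continue after an exacerbation, so step-up prompted by an exacerbation can remove Stiolto follow-up from them.

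The lists also conflict. Two programmers working from different sections could censor different patients, most plainly those with an ICS fill shorter than 30 days.

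**Working it through.** **1. No planned figure to reproduce.** The documents give no rate of ICS addition, switch or discontinuation, and do not size this bias. All rates below are assumptions.

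**2. Does any named sensitivity analysis relax the censoring?**

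| Analysis | What changes | Follows patients past switch or ICS addition? |
|---|---|---|
| 30-day gap | Discontinuation definition | No |
| All available data | Contrasted only with the 12-month limit | No |
| Severity | Outcome definition | No |
| Prognostic covariates | Covariate set | No |
| Bias analysis (9.9) | Not specified | Cannot be told |

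**3. Size when step-up follows underlying risk.** Assumptions: true hazard ratio 1; each patient has a gamma frailty with mean 1 and variance θ (0.5 or 1); the one-year exacerbation risk c is 30% or 50%; 40% discontinue at random in both arms; step-up hazard is proportional to frailty and occurs in Stiolto only, with s the share stepping up within a year.

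Baseline exacerbation hazard: h = [(1 − c)^(−θ) − 1]/θ. Step-up hazard: m = [(1 − s)^(−θ) − 1]/θ.

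Mean frailty among those still at risk at time t is 1/[1 + θ(h + m)t] in Stiolto and 1/(1 + θht) in Trelegy. The apparent hazard ratio at time t is therefore

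HR(t) = (1 + θht) / [1 + θ(h + m)t].

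Example with c = 0.30, s = 0.30, θ = 1: h = m = 1/0.7 − 1 = 0.429. HR(0) = 1; HR(0.5) = 1.214/1.429 = 0.85; HR(1) = 1.429/1.857 = 0.77. The Cox model averages these over the event times, with more weight early. Simulation with 500,000 patients per arm gives 0.888.

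All simulated settings:

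| Step-up in Stiolto at one year | As-treated HR, Stiolto vs Trelegy | Not censored at step-up |
|---|---|---|
| 5% | 0.98–0.99 | 1.00 |
| 10% | 0.97–0.98 | 1.00 |
| 20% | 0.93–0.97 | 1.00 (to 1.005) |
| 30% | 0.89–0.95 | 1.00 (to 1.005) |

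With c = 50% and θ = 1, step-up of 20% in Stiolto and 10% in Trelegy gives 0.97. Equal step-up of 20% in both arms gives about 1.00.

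**4. Size when step-up comes just before the exacerbation.** Suppose a share q of Stiolto first events is lost because an ICS was added shortly before. Then HR ≈ 1 − q. With 3,018 per arm (section 9.5), an assumed 40% with events and two-sided α of 0.05 (assumed from the 95% CI), the number of events is E = 2 × 3,018 × 0.40 × (1 − q/2), and the chance of a false finding for Stiolto is Φ(|ln(1 − q)|√E/2 − 1.96).

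For q = 0.05: E = 2,354; 0.0513 × 48.5/2 = 1.24; Φ(1.24 − 1.96) = 24%.

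| q | HR | False finding for Stiolto |
|---|---|---|
| 2% | 0.98 | 7% |
| 5% | 0.95 | 24% |
| 10% | 0.90 | 71% |
| 20% | 0.80 | over 99% |

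**5. Pneumonia.** With 20–40% of Stiolto patients assumed to add an ICS after an exacerbation, and no true effect, simulated pneumonia hazard ratios were 0.97 to 0.91. This is illustrative only.

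**The case against.** Several points on the other side stand.

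- **Not all censoring is one-sided.** Switch and discontinuation apply to both arms. Appendix 2 lists methylxanthines and "PDE-4 inhibitor (oral") as maintenance medications, so a 30-day add-on to Trelegy can count as a switch. With half the Stiolto step-up hazard in Trelegy, simulated hazard ratios were 0.94 to 0.98 (frailty variance 1–2).
- **The Stiolto phrase may only clarify.** An ICS fill of 30 days or more already meets the switch rule. Stiolto plus an ICS is triple therapy, so stopping on-treatment follow-up there is coherent with the declared design. That does not settle shorter fills, nor make the censoring uninformative.
- **The initial-treatment analysis is not decisive.** A null result there could reflect dilution as well as the removal of selection.

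Three stronger readings are tempting and unsupported.

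- A reader might infer that no analysis could detect the bias. Section 9.9 leaves room for a bias analysis, although its discussion concerns unmeasured confounding and later outcomes. The numbering also passes from 9.7.1 to 9.7.3, so only the visible text can be judged. Claims also continue after step-up while the patient is enrolled.
- A reader might quote a hazard ratio as low as 0.86 with 69% false rejection. That setting needs frailty variance 2, about 25% stepping up within a year (hazard 0.4 × frailty: 1 − 1.8^(−1/2) = 0.25), step-up exactly proportional to exacerbation risk, and no risk-related censoring in Trelegy. The documents establish none of these.
- A reader might set the bias beside the hazard ratio of 0.97 cited in section 9.5. That ratio is triple versus dual therapy; in the direction used here it is 1/0.97 = 1.03. The two are not comparable.

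**Conclusion.** The point holds in limited form. The four follow-up lists disagree on ICS addition, every specified Cox analysis is as-treated, and no visible specified sensitivity analysis relaxes that censoring. The resulting bias can favour Stiolto.

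Its size cannot be derived from the documents. If step-up is 10% or less and only tracks underlying risk, the bias is small (0.97 to 0.99). It becomes material, at 0.95 or lower, if step-up is common or comes shortly before exacerbations, and it grows with stronger frailty. It disappears if risk-related censoring is equal in the two arms. The direction rests on step-up being more frequent, or more closely tied to risk, in Stiolto. The background makes that plausible, but no data in the plan show it.

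**What to change.** 1. Reconcile the lists in 9.1, 9.2.2 and 9.3.1 into one add-on and switch censoring rule, with one fill-length requirement, applied the same way in both arms.
2. Keep the as-treated main analysis.
3. Pre-specify one initial-treatment sensitivity analysis of the exacerbation and pneumonia Cox models. Follow each patient to the event, 12 months, disenrollment or data end, regardless of switch, ICS addition or discontinuation. An as-treated model with inverse-probability-of-censoring weights is an option that would help to separate selection from dilution.
4. Report censoring reasons by arm, with ICS addition shown separately.

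The cost is one further Cox model per endpoint and one table, all on claims already held; weighting would take more programming. The downside is that the initial-treatment analysis mixes treatments and tends toward no difference, so it should be read beside the as-treated result and not in place of it.

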The following outcomes will be measured in the baseline and follow-up periods. The baseline period will include claims occurring on the index date, except for the index medication claims, which will be included in the follow-up period.

- All-cause health care resource utilization: Indicator variables and counts of physician office visits, hospital outpatient visits, ED visits, "other" (non-inpatient) visits, inpatient stays, and pharmacy claims will be created. Other medical visits are a residual category that includes, but is not limited to, services rendered at independent laboratories, assisted living facilities, and by home health providers. An indicator variable will be created to identify inpatient stays with an acute stay during the inpatient stay, the time to first inpatient stay will also be captured. The time to first inpatient stay, the time to first eD visit during follow-up will be captured.
- COPD and/or pneumonia-related health care resource utilization: This utilization will be calculated analogously to all-cause utilization, but restricted to medical claims with a diagnosis for COPD and/or pneumonia, in any position (Appendix 1) and pharmacy claims for a COPD-related treatment (Appendix 2), including COPD-guideline recommended antibiotics (Appendix 3).

- COPD-related health care resource utilization: This utilization will be calculated analogously to all-cause utilization, but restricted to medical claims with a diagnosis for COPD in any position (Appendix 1) and pharmacy claims for a COPD-related treatment (Appendix 2), including COPD-guideline recommended antibiotics (Appendix 3)
- Pneumonia-related health care resource utilization: This utilization will be calculated analogously to all-cause utilization but restricted to medical claims with a diagnosis for pneumonia in any position (Appendix 1).
- COPD or pneumonia-attributable health care resource utilization: This utilization will be calculated analogously to all-cause utilization, but restricted to medical claims with a diagnosis for COPD or pneumonia in the primary position or a diagnosis for acute respiratory failure in the primary position and a diagnosis for COPD or pneumonia in a non-primary position (Appendix 1) and pharmacy claims for a COPD-related treatment (Appendix 2), including COPD-guideline recommended antibiotics (Appendix 3)

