9.7 DATA ANALYSIS

Summary measures will include standard descriptive statistics (e.g., mean, standard deviation, median and range for continuous variables; counts and percentages for categorical variables). However, for any baseline characteristics with significant differences (Standardized differences (SD) greater than 0.10 (10%)) after PSM matching, these characteristics will be included as covariates in the regression models, or we will develop interaction terms to match on or discontinue the study if major channeling (SD>10%) is observed. Basically, a two-step approach: The first step will be to characterize the patients after PS matching to see whether balance can be achieved (based on SD) and at least 2000 patients from the Stiolto cohort can be matched with at least 2000 patients in the Trelegy cohort before proceeding to the second step of doing the comparative analysis. Sensitivity analyses may be performed on a select set of covariates considered to be prognostic factors. In the event of study discontinuation, partial results (all analysis leading up to and including PSM) will be provided in a final report.

A Cox proportional hazards models will be used on the time to first COPD exacerbation with treatment as a covariate. Comparisons will be made between treatment cohorts using HR and will be presented with associated 95% CI. To account for variable lengths of follow-up observation time, population annualized results will be provided (annualized costs [e.g., Sum of total costs/Sum of total follow-up patient years for each cohort]). The annualized cost may be modelled as dependent variable in a Generalized Linear Model with treatment cohort as a covariate and the follow-up patient years as an offset for each cohort.

Comparisons will be made between treatment cohorts and will be presented with associated 95% CI. Additionally, descriptive techniques that account for the length of observation time measure will be used appropriately. Per patient per month calculations will not be performed because of bias concerns. Appropriate tests comparing the Stiolto cohort and the Trelegy cohort (e.g., standardized differences, McNamara's tests, paired t-tests, sign tests) will be used based on the distribution of the measure. Patients not matched will be excluded from the post-match analysis.

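### Sections 9.3 and 9.3.1 conflict on whether the index inhaler fill counts in follow-up cost and dispensing; coding the 9.3.1 dates literally would drop one fill per patient

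*Combined protocol and SAP*

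**What the plan says.** Section 9.3, introducing the HCRU and cost outcomes, places claims dated on the index date in baseline, "except for the index medication claims, which will be included in the follow-up period". The same sentence appears again in 9.3 under clinical characteristics. The baseline respiratory medication variables in 9.3 likewise leave out the claims that define the index therapy.

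Section 9.3.1 defines baseline as "The 12 months prior to and including the index date" and starts the outcome window the next day: "index date +1 through index date +365) will be used to assess exacerbation, pneumonia, HCRU and cost outcomes". It states no exception for the index fill. Earlier in the same section, dispensing is measured "over a follow-up period, beginning the index date and lasting up to one year from index date".

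On-treatment time ends at discontinuation, with "discontinuation date = runout prior to the gap in therapy". Section 9.7 annualizes as "Sum of total costs/Sum of total follow-up patient years for each cohort". Under 9.3, total cost is pharmacy plus medical cost. Section 9.3.2.2 lists annual costs and dispensings per year under the secondary outcomes.

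**The concern.** The index date is the date of the first Stiolto or Trelegy claim, so every patient's index fill falls on day 0. The 9.3.1 outcome window runs from day +1. A programmer who codes those offsets, and who also follows 9.3 in keeping the fill out of baseline, counts it in neither period. The days it supplies are still treated time, so they remain in the denominator. One fill of cost is lost per patient, whether treatment lasted one month or twelve.

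At stake are annualized pharmacy cost, total cost, COPD-related cost and dispensings per year. Because the loss is a fixed count per patient, it weighs more on a cohort with shorter treatment or fewer, longer fills. Two drugs with the same cost per treated day could then appear to differ.

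**Working it through.** The plan states no figure to reproduce. The check is a day count followed by the section 9.7 formula.

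**Windows (9.3.1).** Baseline runs from day -364 to day 0: 0 - (-364) + 1 = 365 days. The outcome window runs from day +1 to day +365: 365 days. Day 0 lies in baseline only, and 9.3 removes the index fill from baseline.

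**Assumptions (not in the protocol).** Fills of equal days' supply S, price 1 per fill, no gaps, and follow-up ending at run-out unless stated.

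**Loss of one fill.** With mean fills *m* per patient, mean follow-up is *m*S days.
- Index fill counted (9.3 rule): annual rate = *m* × 365/(*m*S) = 365/S, which is 12.17 for S = 30.
- Index fill lost (literal 9.3.1): (*m* - 1) × 365/(*m*S).
- Relative understatement: 1/*m*. This is exact at cohort level because 9.7 takes a ratio of sums.

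For S = 30, the loss is 365/(mean follow-up days) fills per year:

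| Mean follow-up (days) | Fills per year lost | Share of 12.17 |
|---|---|---|
| 60 | 6.08 | 50% |
| 90 | 4.06 | 33% |
| 120 | 3.04 | 25% |
| 180 | 2.03 | 17% |
| 365 | 1.00 | 8% |

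**Between-drug ratio of index-drug cost, equal price.**
- Mean fills 4 and 5: counted, 1.00; lost, (3/4)/(4/5) = 0.75/0.80 = 0.94.
- Simulated cohorts, 30-day fills, constant refill probability, follow-up capped at day 365: with mean follow-up of about 99 and 140 days, counted 0.99 and lost 0.88; with about 75 and 140 days, counted 0.99 and lost 0.75.
- Equal persistence and days' supply: both cohorts shrink by the same factor. The ratio is unchanged, but any absolute difference in index-drug cost shrinks by that factor.

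**Dilution.** If index-drug cost is a share *s* of total cost, total cost is understated by *s*/*m*. The protocol does not give *s*.

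**Residual error when the fill is counted.** A fill bought near the end of follow-up is charged whole.
- 30-day fills to day 365: fills on days 0, 30, …, 360 make 13, against 12.17 used (+6.8%). Dropping the index fill gives 12 (-1.4%).
- 90-day fills to day 365: 5 against 4.06 (+23.3%). Dropping gives 4 (-1.4%).
- Simulated cohorts, refill probability 0.4 to 0.9, no other censoring: 0.0% to +3.3% with 30-day fills and +1.5% to +17.8% with 90-day fills. Dropping the fill in the same cohorts gives about -60% to -11% for both supplies.

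**End of person-time.** Section 9.7.1 speaks of "allowing a grace period of 45 days following the end of days' supply to account for intermittent use", whereas 9.3.1 ends treatment at run-out. If the 45 days were added to the denominator, the counted rate would be 30/75 of the supplied rate for one 30-day fill (-60%) and 180/225 for six (-20%). The end date therefore matters as well as the start.

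**The case against.** The strongest reply is that the plan already answers the question. Section 9.3 names this very claim, says twice that it belongs to follow-up, and does so once in the passage that introduces the HCRU and cost outcomes. Section 9.3.1 itself measures dispensing from the index date. On an ordinary reading the day +1 window is general and 9.3 is the specific exception, so the fill is counted. This reading is reasonable and probably intended. But nothing in the protocol says which rule prevails, and 9.3.1 supplies the exact day offsets that a program would use, with one window for events and costs alike.

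The reply is also right on size. The fill counts and follow-up times above are assumed. They concern index-drug cost, not total cost. For patients treated to day 365, dropping the fill lands nearer the supply actually used than counting it does.

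A reader might go further and infer that the planned cost comparison is biased, or that it favours one drug. The documents do not support that. It would require the literal 9.3.1 reading and also a difference in persistence or days' supply between cohorts, and the protocol reports neither of these, nor price per fill.

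**Conclusion.** The inconsistency is real and should be resolved before programming. If the 9.3.1 dates are applied literally, annualized index-drug cost and dispensings are understated by about 1/(mean fills) when follow-up ends at run-out. With 30-day fills that is 50% to 17% for mean follow-up of 60 to 180 days. These are illustrations under stated assumptions, not estimates for this study. Distortion of the between-drug ratio is conditional on differing persistence or days' supply, and its direction cannot be told from the protocol. Inpatient, ED and outpatient visit counts and the exacerbation and pneumonia time-to-event analyses do not depend on the index fill. The point is confined to the secondary pharmacy, COPD-related and total cost outcomes and the dispensing counts.

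**What to change.** In section 9.3.1, carry over the 9.3 exception: the HCRU, cost and dispensing numerators comprise the index medication claim plus all claims from index date +1 to censoring, and person-time runs from the index date to the stated censoring date. Keep index date +1 as the start for exacerbation and pneumonia events. Apply the same rule to the medication counts in 9.3.2.2. State the censoring date used for the denominator, so that the run-out wording in 9.3.1 and the grace-period wording in 9.7.1 are reconciled.

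The cost is a sentence or two and one date condition in the program, and the rule adopted is the sponsor's own. There is a small downside: counting whole fills overstates cost somewhat when follow-up ends mid-supply, more so with 90-day fills. The plan should say so, and reporting the distribution of days' supply by cohort would let a reader judge it.
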